9.7.4. Data Tabulation

The following outcomes/measurements of interest will be analysed:

- Patients' demographics (age and gender) at baseline
- Relevant comorbidities
- Medical history: disease diagnoses (using appropriate disease classification)
- Concomitant ADMs
- Other drug exposures (main therapeutic classes)
- Average daily dosage of prescriptions
- Prescriptions in combination with other ADMs

These characteristics will be described for overall patients initiated with dulaglutide and in the subgroups of interest corresponding to dulaglutide initiators. Some characteristics of dulaglutide initiators will be described at both the index date and the baseline period, for example, concomitant medications will be defined as those prescriptions recorded at the index date of dulaglutide initiation, while medication history will be defined as those medications which were recorded during the 6-month baseline period prior to dulaglutide initiation.

Note that subgroups will not be mutually exclusive: a patient could be part of more than one subgroup (for example, elderly patients ≥ 75 years and with hepatic disease). The column 'All' in [Table 9.7.4-1](#) will include the results corresponding to the overall data set and not the sum of the results of each subgroup. It also includes patients who are not categorised in any of the subgroups.

Table 9.7.4-1. Mock Table for the Description of the Use of Dulaglutide - Primary Objective: Description of the Use of Dulaglutide per Subgroups

Dulaglutide Country: Sweden	Subgroups of interest				
	1. Patients with severe renal failure (N=xx)	2. Patients with hepatic disease (N=xx)	...	9. Patients with off-label use (N=xx)	10. All (N=xx)
Outcomes/Measurements of interest					
Age (ranges)					
Missing					
< 18 years	xx (xx.x%)	xx (xx.x%)		xx (xx.x%)	xx (xx.x%)
0-4	xx (xx.x%)	xx (xx.x%)		xx (xx.x%)	xx (xx.x%)
5-9	xx (xx.x%)	xx (xx.x%)		xx (xx.x%)	xx (xx.x%)
10-14	xx (xx.x%)	xx (xx.x%)		xx (xx.x%)	xx (xx.x%)
15-17	xx (xx.x%)	xx (xx.x%)		xx (xx.x%)	xx (xx.x%)
18-44 years	xx (xx.x%)	xx (xx.x%)		xx (xx.x%)	xx (xx.x%)
45-64 years	xx (xx.x%)	xx (xx.x%)		xx (xx.x%)	xx (xx.x%)
65-74 years	xx (xx.x%)	xx (xx.x%)		xx (xx.x%)	xx (xx.x%)
≥75 years	xx (xx.x%)	xx (xx.x%)		xx (xx.x%)	xx (xx.x%)
Mean (SD)					
Min-Max					
Median [Q1- Q3]					
Gender					
Missing	xx (xx.x%)	xx (xx.x%)		xx (xx.x%)	xx (xx.x%)
Male	xx (xx.x%)	xx (xx.x%)		xx (xx.x%)	xx (xx.x%)
Female	xx (xx.x%)	xx (xx.x%)		xx (xx.x%)	xx (xx.x%)
Medical history					
T2DM duration: Time since diagnosis:					
Missing	xx (xx.x%)	xx (xx.x%)		xx (xx.x%)	xx (xx.x%)
> 1 year	xx (xx.x%)	xx (xx.x%)		xx (xx.x%)	xx (xx.x%)
[1-5	xx (xx.x%)	xx (xx.x%)		xx (xx.x%)	xx (xx.x%)
> 5 years	xx (xx.x%)	xx (xx.x%)		xx (xx.x%)	xx (xx.x%)
Mean (SD)					
Min-Max					
Median [Q1- Q3]					
T2DM treatment duration:					
Missing	xx (xx.x%)	xx (xx.x%)		xx (xx.x%)	xx (xx.x%)
> 1 year	xx (xx.x%)	xx (xx.x%)		xx (xx.x%)	xx (xx.x%)
[1-5]	xx (xx.x%)	xx (xx.x%)		xx (xx.x%)	xx (xx.x%)
> 5 years	xx (xx.x%)	xx (xx.x%)		xx (xx.x%)	xx (xx.x%)
Mean (SD)					
Min-Max					
Median [Q1- Q3]					

Mock Table for the Description of the Use of Dulaglutide - Primary Objective: Description of the Use of Dulaglutide per Subgroups

Dulaglutide Country: Sweden	Subgroups of interest				
Outcomes/Measurements of interest	1.Patients with severe renal failure (N=xx)	2.Patients with hepatic disease (N=xx)	...	9.Patients with off-label use (N=xx)	10.All (N=xx)
Comorbidities	xx (xx.x%)	xx (xx.x%)		xx (xx.x%)	xx (xx.x%)
Obesity Status (by BMI)					
Missing	xx (xx.x%)	xx (xx.x%)		xx (xx.x%)	xx (xx.x%)
<18.5 kg/m ²	xx (xx.x%)	xx (xx.x%)		xx (xx.x%)	xx (xx.x%)
Normal: 18.5-25 kg/m ²	xx (xx.x%)	xx (xx.x%)		xx (xx.x%)	xx (xx.x%)
>25-30 kg/m ²	xx (xx.x%)	xx (xx.x%)		xx (xx.x%)	xx (xx.x%)
>30 kg/m ²	xx (xx.x%)	xx (xx.x%)		xx (xx.x%)	xx (xx.x%)
Mean (SD)					
Min-Max					
Median [Q1- Q3]					
Hypertension	xx (xx.x%)	xx (xx.x%)		xx (xx.x%)	xx (xx.x%)
Dyslipidemia	xx (xx.x%)	xx (xx.x%)		xx (xx.x%)	xx (xx.x%)
Macrovascular complications:					
Ischaemic heart disease	xx (xx.x%)	xx (xx.x%)		xx (xx.x%)	xx (xx.x%)
Stroke	xx (xx.x%)	xx (xx.x%)		xx (xx.x%)	xx (xx.x%)
Peripheral arterial obstructive disease	xx (xx.x%)	xx (xx.x%)		xx (xx.x%)	xx (xx.x%)
Microvascular complications:					
Diabetic neuropathy	xx (xx.x%)	xx (xx.x%)		xx (xx.x%)	xx (xx.x%)
Diabetic retinopathy	xx (xx.x%)	xx (xx.x%)		xx (xx.x%)	xx (xx.x%)
Diabetic nephropathy	xx (xx.x%)	xx (xx.x%)		xx (xx.x%)	xx (xx.x%)
Solid tumours:					
Liver	xx (xx.x%)	xx (xx.x%)		xx (xx.x%)	xx (xx.x%)
Pancreas	xx (xx.x%)	xx (xx.x%)		xx (xx.x%)	xx (xx.x%)
Endometrium	xx (xx.x%)	xx (xx.x%)		xx (xx.x%)	xx (xx.x%)
Colon	xx (xx.x%)	xx (xx.x%)		xx (xx.x%)	xx (xx.x%)
Rectum	xx (xx.x%)	xx (xx.x%)		xx (xx.x%)	xx (xx.x%)
Breast	xx (xx.x%)	xx (xx.x%)		xx (xx.x%)	xx (xx.x%)
Bladder	xx (xx.x%)	xx (xx.x%)		xx (xx.x%)	xx (xx.x%)

Mock Table for the Description of the Use of Dulaglutide - Primary Objective: Description of the Use of Dulaglutide per Subgroups

Dulaglutide Country: Sweden	Subgroups of interest				
Outcomes/measurements of interest	1. Patients with severe renal failure (N=xx)	2. Patients with hepatic disease (N=xx)	...	9. Patients with off-label use (N=xx)	10. All (N=xx)
Dulaglutide exposure Average daily dose Missing Mean (SD) Min-Max Median [Q1- Q3]	xx (xx.x%)	xx (xx.x%)		xx (xx.x%)	xx (xx.x%)

Mock Table for the Description of the Use of Dulaglutide - Primary Objective: Description of the Use of Dulaglutide per Subgroups

Dulaglutide Country: Sweden	Subgroups of interest				
	1. Patients with severe renal failure (N=xx)	2. Patients with hepatic disease (N=xx)	...	9. Patients with off-label use (N=xx)	10. All (N=xx)
Concomitant medications (at index date) Anti-diabetic treatments:	xx (xx.x%)	xx (xx.x%)		xx (xx.x%)	xx (xx.x%)

 • Insulins and analogues (short- and long-acting, for injection and inhalation) (meal-time, for example, Insulin Lispro; and basal, for example Insulin Glargine). • Biguanides (for example, Metformin) • Sulfonylureas (for example, Glipizide) • Alpha-glucosidase inhibitors (for example, Acarbose) • Thiazolidinediones (for example, Pioglitazone) • Dipeptidyl peptidase-4 inhibitors (for example, Sitagliptin) • Sodium glucose cotransporter-2 (SGLT2) inhibitors (for example, Empagliflozin) • Other GLP-1 RA • Meglitinides (for example, Repaglenide) • Amylin analogues (for example, Pramlintide) 	xx (xx.x%)	xx (xx.x%)		xx (xx.x%)	xx (xx.x%)
And:					

 • Single-pill combinations of oral ADMs • Single-injection combinations of insulin and GLP-1 RA (for example, Insulin Degludec and Liraglutide) 	xx (xx.x%)	xx (xx.x%)		xx (xx.x%)	xx (xx.x%)
	xx (xx.x%)	xx (xx.x%)		xx (xx.x%)	xx (xx.x%)

Concomitant medications (at index date) Other treatments (main classes)	xx (xx.x%)	xx (xx.x%)		xx (xx.x%)	xx (xx.x%)
Dulaglutide off-label use - Patients without T2DM - Patients with T2DM for whom dulaglutide was prescribed as first-line therapy	xx (xx.x%) xx (xx.x%) xx (xx.x%)	xx (xx.x%) xx (xx.x%) xx (xx.x%)		xx (100%) xx (xx.x%) xx (xx.x%)	xx (xx.x%) xx (xx.x%) xx (xx.x%)
Medication history (at baseline period) Anti-diabetic treatments: - specific classes	xx (xx.x%)	xx (xx.x%)		xx (xx.x%)	xx (xx.x%)
Medication history (at baseline period) Other treatments: - specific classes	xx (xx.x%)	xx (xx.x%)		xx (xx.x%)	xx (xx.x%)

Abbreviations: ADM= anti-diabetes medications; BMI= body mass index; GLP-1 RA= glucagon-like peptide-1 receptor agonists; T2DM= type 2 diabetes mellitus.

Note: the table structure may be adjusted in the final study report.

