The rationale for this study is the need to gain knowledge about dulaglutide utilisation in real world conditions, as well as information on off-label use, medication errors, and the use in subpopulations of patients for which little data exist (i.e., patients with severe renal failure, heart failure, hepatic disease, or severe gastrointestinal disease; children and adolescents with T2DM < 18 years of age; elderly \geq 75 years; and pregnant and breastfeeding women).

8. Research Question and Objectives

The purpose of this study is to describe how dulaglutide is used among different patient groups in European countries.

Primary objective:

To describe the frequency of dulaglutide use in the population and characterise by age, gender, main co-morbidities and main co-prescriptions overall and within the following subgroups of interest:

- Populations of interest:
 - Patients with severe renal failure
 - Patients with hepatic disease
 - Patients with heart failure
 - Patients with severe gastrointestinal disease
 - Children and adolescents <18 years of age
 - Elderly patients ≥ 75 years
 - Pregnant and breastfeeding women
- Medication use:
 - Medication errors
 - Off-label use

Secondary objective:

To describe the off-label use among each subgroup of populations of interest.

9. Research Methods

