- Any record of pregnancy or breast feeding at the time of treatment initiation.

Patients with medication errors:

- Prescribed and/or administered > 1 dose per week of dulaglutide (6).
- The number of doses/week will be calculated by measuring the time span between the current prescription and the next one (in weeks) and dividing the number of injections prescribed in the current prescription by this time span. This number of doses/week will be used in the cross sectional study as an attribute of the prescription to assess the occurrence of medication errors as described above.

Patients with off-label use:

- Prescribed dulaglutide with no diagnosis of T2DM as defined above, at the beginning of this list of subgroups of populations.
- Prescribed dulaglutide with a diagnosis of T2DM as defined above and without a record of other ADMs during the 6-month baseline period, i.e. dulaglutide was prescribed as first-line therapy.

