
Other comorbidities frequent in T2DM patients: Dyslipidemia Hypertension
 
Macrovascular complications: Ischaemic heart disease
 
Stroke Peripheral arterial obstructive disease
 
Microvascular complications: Diabetic neuropathy Diabetic retinopathy Diabetic nephropathy
	
ICD-10 codes E78 or lipid modifying agents (ATC C10) ICD-10 codes I10-I15 or antihypertensives (ATC C02, C03, C04, C07, C08, C09) with no angina pectoris (I20, I25)
 
ICD-10 codes I20-I25 or antiangina agents (ACT C01D, C07, C08, C09) I61-I64 I70.2
 
G62.9 H36.0 N08.3

Solid tumours (Cancer)
 
 • liver • pancreas • endometrium • colon • rectum • breast • bladder 	
ICD-10 codes C220-C229 ICD-10 codes C250-C259 ICD-10 code C541 ICD-10 codes C182-C189 ICD-10 code C20 ICD-10 codes C500-C509 ICD-10 codes C670-C679

Dulaglutide dose: per 0.5 ml
	
Dose: 0.75 mg / week 1.5 mg / week >1.5 mg / week

Variables, Subgroups and Measurements of Interest

Variable, subgroup or outcome/measurement	Definition and categories*
Concomitant medications for T2DM , at index date of dulaglutide initiation	
 • Molecule: INN/brand name • ATC code or associated medcode for AMD 
A10A Insulins and analogues
 
 ○ A10AB Insulins and analogues for injection, fast-acting ○ A10AC Insulins and analogues for injection, intermediate-acting ○ A10AD Insulins and analogues for injection, intermediate- or long-acting combined with fast-acting ○ A10AE Insulins and analogues for injection, long-acting ○ A10AF Insulins and analogues for inhalation 
A10B Blood glucose lowering drugs, excluding insulins
 
 ○ A10BA Biguanides ○ A10BB Sulfonylureas ○ A10BD Combinations of oral blood glucose lowering drugs ○ A10BF Alpha glucosidase inhibitors ○ A10BG Thiazolidinediones ○ A10BH Dipeptidyl peptidase 4 (DPP-4) inhibitors ○ A10BX Other blood glucose lowering drugs (exenatide, liraglutide, lixisenatide, albiglutide), excluding insulins 
A10P SGLT2 Inhibitors

Other concomitant medications , at index date of dulaglutide initiation	
 • ATC codes or associated medcode for main pharmacological classes.
History of medications for T2DM , during 6-month baseline period	
 • ATC code or associated medcode for anti-diabetes medications (see above)

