9.4.3. NPR and SPDR in Sweden

Swedish data combine data from the NPR, covering all specialist and hospital care in Sweden, and the SPDR, covering all drugs dispensed at pharmacies in Sweden. The national registers are

updated at least quarterly. These longitudinal data enable to find out comorbidities and historical clinical information on the subjects treated for their T2DM in a hospital, as well as drug prescription details (both primary and secondary care). Prescriptions are not formally linked to an ICD-10 code, but clinical input could provide rationale for linking prescriptions and diagnosis made in secondary care. However, information on patient anthropometric data (height, weight, BMI) are not available through the databases, nor are lab results and clinical measurements such as HbA1c, blood pressure and blood lipid levels.

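### Concomitant medication is counted only from records on the index date, so drugs prescribed earlier and still in use are under-counted by an unknown, possibly large amount

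*Protocol*

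**What the plan says.** The primary objective in Section 8 is to describe dulaglutide use and to "characterise by age, gender, main co-morbidities and main co-prescriptions overall and within the following subgroups of interest". Section 9.3.1 and the outcome list in Section 9.7.4 carry this forward as concomitant anti-diabetes drugs, other drug exposures, and prescribing in combination with other anti-diabetes drugs.

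The operational rule is in Section 9.7.4: "concomitant medications will be defined as those prescriptions recorded at the index date of dulaglutide initiation". Table 9.3.2-1 sets the same time point, "at index date of dulaglutide initiation", both for diabetes drugs and for other drugs. The concomitant-medication rows of mock Table 9.7.4-1 are also labelled as index-date rows.

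The second half of the same sentence in Section 9.7.4 defines a separate measure: "medication history will be defined as those medications which were recorded during the 6-month baseline period prior to dulaglutide initiation". The mock table reports it in its own rows, for anti-diabetic and for other treatments.

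First-line off-label use is defined in Section 9.3 by a type 2 diabetes diagnosis "without a record of other ADMs during the 6-month baseline period".

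**The concern.** Long-term drugs are supplied for weeks at a time. Take a patient whose metformin was prescribed three weeks before the first dulaglutide prescription, with supply still in hand. That patient may have no metformin record on the index date, and the rule then counts metformin as not concomitant. For ongoing drugs the error runs only downwards, and a larger sample does not reduce it.

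The table would also be hard to read. This patient appears under medication history and is not first-line, yet shows no concomitant anti-diabetes drug. History does not settle what is taken together with dulaglutide, since a drug that dulaglutide replaced (another GLP-1 RA, say) enters it exactly as a continued drug does.

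What an index-date record means also depends on the source. Section 9.4.3 describes "the SPDR, covering all drugs dispensed at pharmacies in Sweden", so in Sweden the record is a dispensing, whereas Table 9.5.2-1 lists no pharmacy information for France, Germany or the UK. The same-day share may therefore differ by database.

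At stake is the co-prescription part of the primary objective. The rule is fixed in the protocol, so an SAP that follows it inherits the problem, and Section 9.9 does not mention it.

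**Working it through.** **The protocol's own yardstick.** Section 9.5.1 uses n = p(1-p)z²/e² with p = 0.5 and 95% confidence. This gives 384.1 for ±5 points, 1067.1 for ±3 and 96.04 for ±10, against the stated 384, 1066 and 97. They agree apart from rounding. At the planned minimum of 100 patients per country, the half-width is 1.96 × √(0.25/100) = 9.8 points, so the per-country yardstick is about 10 points.

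**Inputs that the protocol does not give (assumptions).**
- L, the renewal interval of an ongoing drug: 28 to 90 days.
- s, the share of ongoing users re-prescribed on the index day because renewal coincides with initiation: 0 to 90%.
- p, true co-use of the drug class: 50% or 70%.

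**Model.** The remaining users, a share 1-s, have renewal dates spread evenly over L days, so a fraction 1/L of them falls on the index day by chance. The share of ongoing users captured is

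c = s + (1-s)/L,

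recorded co-use is p × c, and the under-count is p × (1-c). The model is per drug class, as the mock table's rows are.

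**Results for p = 70%** (L = 30 / L = 90):

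| s | captured share | recorded co-use | under-count, points |
|---|---|---|---|
| 0 | 3.3% / 1.1% | 2.3% / 0.8% | 67.7 / 69.2 |
| 25% | 27.5% / 25.8% | 19.3% / 18.1% | 50.7 / 51.9 |
| 50% | 51.7% / 50.6% | 36.2% / 35.4% | 33.8 / 34.6 |
| 75% | 75.8% / 75.3% | 53.1% / 52.7% | 16.9 / 17.3 |
| 90% | 90.3% / 90.1% | 63.2% / 63.1% | 6.8 / 6.9 |

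The loss thus runs from about 10% of ongoing users (s = 90%) to about 99% (s = 0, L = 90). It depends almost wholly on s; L matters little once s is 25% or more.

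**Same-day share needed to keep the under-count within 10 points.** Solve p(1-s)(1-1/L) = 0.10.
- p = 70%, L = 30: 1-s = 0.10/(0.70 × 0.967) = 0.148, so s = 85.2%. L = 90 gives 85.6%.
- p = 50%: s = 79.3% (L = 30) and 79.8% (L = 90).

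Below these levels the bias exceeds the sampling error that the study was sized for.

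**Alternative rules in the same model.** A look-back of W days captures min(1, W/L). A 90-day look-back captures all ongoing users for L up to 90 days. A 30-day look-back captures 100%, 50% and 33% for L = 30, 60 and 90. A supply-overlap rule captures all of them by construction.

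**The case against.** The strongest reply is that the plan reports two measures side by side. Earlier prescriptions appear as medication history in the same table and by the same subgroups. A reader might infer that ongoing treatment is lost from the study, and that is not so. What stands is that the history row gives an upper figure for drugs already in use; it does not measure co-use.

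A reader might also infer that established combination users will be classed as first-line monotherapy and inflate the off-label count. The documents do not support this, because that definition uses the 6-month window.

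Next, drugs prescribed on the same day is a literal reading of co-prescription in a study described as cross-sectional. That is fair, and it is why the same-day figure should be kept. But the protocol calls this quantity concomitant medication, and a same-day record answers a narrower question than that label suggests.

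It is tempting to read differences between countries as artefact. Section 9.7.1 rules out pooling because the databases differ, and plans no inferential analysis. No formal comparison is planned that the bias could distort; it remains only a caution for anyone reading the country tables together.

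Finally, an overlap rule needs days' supply. Table 9.4.5-1 lists dosage and exposure duration as available in all five databases, but does not say that this covers every co-medication. Table 9.3.2-1 lists only names and codes for these drugs, and Section 9.9.1 treats SIDIAP dispensing as a proxy for doses administered. The change looks feasible, but the feasibility assessment should confirm it.

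**Conclusion.** The point holds as a definition problem with a known direction and an unknown size. As written, concomitant anti-diabetes drugs and combination prescribing are under-counted for drugs prescribed earlier and still in use, and no other row in the table recovers the figure. With true co-use of 70%, about 85-86% of ongoing users would have to be re-prescribed on the index day for the under-count to stay within 10 points; with 50%, about 79-80%.

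These thresholds rest on assumed renewal intervals and co-use, and on evenly spread renewal dates among users not renewed at initiation. The extreme result, with capture of only 1-4% of ongoing users, requires renewals to be unrelated to the initiation visit. Nothing in the protocol supports that, so a severe under-count is possible but not established.

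**What to change.** In Section 9.7.4, Table 9.3.2-1 and Table 9.7.4-1, define a concomitant medication as one with either:
- a prescription or dispensing on the index date; or
- an earlier prescription or dispensing whose supply, with a stated grace period, reaches the index date.

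Where days' supply is not available, use a stated look-back, for example a record in the 90 days up to and including the index date. Do not also require a record after the index date, since that would drop true users whose next prescription is late or not captured.

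Keep same-day prescription as a separate row and add the point to the limitations in Section 9.9. Check in the feasibility assessment which databases hold days' supply for co-medications, and state per database which rule applies.

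The cost is wording and some programming. The downside is small: a few drugs just stopped or replaced at initiation will be counted as concomitant.

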9.2.3. Population of Interest

The population of interest includes all patients receiving an initiation of dulaglutide during the observation period for each wave of the study. The use of dulaglutide will be analysed overall and within the following subgroups of patients.

- Populations of interest:

- Patients with severe renal failure
 - Patients with hepatic disease
 - Patients with heart failure
 - Patients with severe gastrointestinal disease
 - Children and adolescents <18 years of age
 - Elderly patients ≥ 75 years
 - Pregnant and breastfeeding women
- Medication use:
 - Medication errors
 - Off-label use

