9.3. Variables

Regardless of the coding system used in the database, different populations and subgroups of interest are defined as follows:

Treatment initiation with dulaglutide:

- any record of prescription of dulaglutide during the observation period without prior record of prescription of the same product in the available patient's history
- if no prior history is available to check the above criteria, the prescription is not considered as an initiation

Patients presenting with T2DM:

- with any recorded diagnosis code for T2DM
- or with any recorded treatment code for an ADM other than insulin
- or, with any recorded treatment code for insulin initiated at age >30 (defined as no record of insulin therapy during 6 months prior to first record of insulin treatment)
- or with any record of unspecified diabetes mellitus diagnosis at age >30 and without history of insulin therapy (defined as no record of insulin therapy during 6 months prior to first record of diabetes diagnosis),
- a sensitivity analysis will be conducted to determine the age threshold mentioned above (see section 9.7.3 Sensitivity analysis).

Patients with severe renal failure:

- with a recorded diagnosis of severe renal failure
- or with a recorded glomerular filtration rate (eGFR) value <30 ml/min/1.73 m²

Patients with hepatic disease:

- with a recorded diagnosis of any hepatic disorder

Patients with heart failure:

- with a recorded diagnosis of heart failure

Patients with severe gastrointestinal disease:

- with a recorded diagnosis of any of the following conditions:
 - cancer of the gastrointestinal tract,
 - diseases of the oesophagus,
 - active ulcer at the time of drug initiation (gastric, duodenal, gastro-jejunal, peptic ulcer of unspecified site),
 - active haemorrhagic gastritis, chronic atrophic gastritis, adult hypertrophic pyloric stenosis, obstruction of duodenum, and other motility disorders,
 - digestive fistula,
 - Crohn's disease, ulcerative colitis,
 - diverticular disease of the intestine,
 - severe vomiting, severe diarrhoea and severe constipation
 - motility disorders, including ileus, gastroparesis, et cetera,
 - infectious and inflammatory situations (appendicitis, cholecystitis, cholangitis).

Children and adolescents:

- Age < 18 at the time of treatment initiation
(subgroups of analysis: 0-4, 5-9, 10-14, and 15-17 years old).

Elderly:

- Age \geq 75 at the time of treatment initiation.

Pregnant and breastfeeding women:

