9.3.2. Collected variables

To assess the above subgroups and measurements of interest, several variables will be extracted from each database whenever available: demographics, medical history, treatment, clinical and clinical laboratory data on patients. These variables along with their corresponding International Classification of Disease, 10th version (ICD-10) codes are presented in this protocol (Table 9.3.2-1). For CPRD database, the corresponding Read codes will be specified in the statistical analysis plan (SAP).

Table 9.3.2-1. Variables, Subgroups and Measurements of Interest in Dulaglutide Initiators

Variable, subgroup or outcome/measurement	Definition and categories*
Patients demographics at initiation of dulaglutide use: Age Gender BMI categories, Countries	< 18, 18-44, 45-64, 65-74, ≥75 years Male or Female Weight (kg) / Height (cm) ² < 18.5, 18.5-25, 26-30, > 30 kg/m ² UK, Germany, Sweden (or Spain and France)
Co-morbidities , at initiation of treatment to identify the subgroups of interest: 
 • History of severe renal failure • Heart failure • Hepatic disease • Severe gastrointestinal disease • Children and adolescents • Elderly • Pregnant women • Breastfeeding women 	ICD-10 code N18.5, N18.5 ICD-10 codes I50, I11, I13 ICD-10 codes B18, K70-K77, C22 ICD-10 codes C15-C26 K22.0, K22.1, K22.2 -K22.6, K23-K28, K29.0, K29.4 K50, K51, K55, K57 Age < 18 (subgroups: 0-4, 5-9, 10-14, 15-17 years) Age ≥ 75 ICD-10 codes: A34, E23.0, F53, M83, O00-O99, O24.1, O24.3, O24.9, Z32-Z36, Z39 Z39.1
Lab tests values (if available): 
 • Haemoglobin A1c (HbA1c) • e-GFR • Serum Creatinine Urine albumin/creatinine ratio (UACR) 
 • LDL-C (LDL-cholesterol) • HDL-C (HDL-cholesterol) • AST/ALT • Bilirubin • Beta hCG 	Abnormal values: < 6.5%, ≥6.5% eGFR value < 30 ml/min/1.73 m ² < 120, ≥120 µmol/L or mg/dL (male) < 100, ≥100 µmol/L or mg/dL (female) UACR >30 mg/g: albuminuria present: < 1.6, ≥ 1.6 g/L < 0.35 g/L, ≥0.35 g/L ≤ 2 or > 2 times upper limit of the normal range < 2, >7mg/L Positive

Variables, Subgroups and Measurements of Interest

Variable, subgroup or outcome/measurement	Definition and categories*

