9.7.2. Subgroups and Outcomes/Measurements Analysed to Answer the Endpoints

Analyses will be performed in the 9 subgroups of interest (See Section 9.2.3).

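### The mock table's BMI classes, including the one labelled 'Normal', have no age limit and so also apply to the under-18 subgroup (minor, one descriptive row)

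*Protocol*

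**What the plan says.** Section 9.7.4, Table 9.7.4-1, has a row headed "Obesity Status (by BMI" with four classes: below 18.5, "Normal: 18.5-25 kg/m" squared, above 25 to 30, and above 30. The same block has a line for missing values and gives the mean, SD, minimum, maximum, median and quartiles.

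Section 9.3.2, Table 9.3.2-1, lists much the same bins as BMI categories, "18.5-25, 26-30, > 30 kg/m" squared, preceded by a class below 18.5. It does not use the word 'Normal'. Neither table sets an age condition, and no other section supplies one.

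Section 9.2.3 names "Children and adolescents <18 years of age" as a population of interest. Section 9.3 divides them further: "subgroups of analysis: 0-4, 5-9, 10-14, and 15-17 years old". Section 9.2.2 applies no exclusion criteria.

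On the reach of the table, section 9.7.2 states: "Analyses will be performed in the 9 subgroups of interest". Section 9.7.4 says the characteristics are "described for overall patients initiated with dulaglutide and in the subgroups of interest". A note under the table adds that "the table structure may be adjusted in the final study report".

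**The concern.** A fixed BMI scale with a 'Normal' band suits patients whose growth is complete. BMI changes with age in childhood, so a value that is unremarkable in a small child can fall below 18.5, and a high value for that age can fall inside 18.5-25. The row could therefore mislead in either direction in the younger age bands.

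Children and adolescents are a group about which the study was set up to learn more, so their column will be read with attention. What is at stake is the reading of this one row in that column, plus a very small contribution to the overall column and to any other subgroup column that contains a child.

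**Working it through.** The Protocol gives no figure for this row, so there is none to reproduce. The check has three parts.

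**1. Does the row reach children?** Four statements, taken together, settle it.
- Under-18s are one of the nine subgroups (sections 9.2.3 and 9.7.2).
- Nothing excludes them (section 9.2.2).
- The tabulated characteristics are described overall and by subgroup (section 9.7.4).
- Subgroups may overlap, and the overall column holds every eligible patient (section 9.7.4).

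The printed table abbreviates the middle columns with dots, but the text makes clear that the paediatric column is among them.

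**2. What do the cut-offs mean for a small child?** The class limits convert to weight by weight = BMI x height squared. Only the heights are assumed.

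| Height | Height squared | Weight at BMI 18.5 | Weight at BMI 25 |
|---|---|---|---|
| 1.00 m | 1.0000 | 18.5 kg | 25.0 kg |
| 1.10 m | 1.2100 | 22.4 kg | 30.3 kg |
| 1.25 m | 1.5625 | 28.9 kg | 39.1 kg |

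The next step assumes weights as well. They are illustrations and do not come from the Protocol.
- 1.00 m, 14 to 17 kg: 14/1.00 = 14.0 to 17/1.00 = 17.0, all in the class below 18.5.
- 1.10 m, 16 to 20 kg: 16/1.21 = 13.2 to 20/1.21 = 16.5, all below 18.5.
- 1.25 m, 22 to 27 kg: 22/1.5625 = 14.1 to 27/1.5625 = 17.3, all below 18.5.
- 1.25 m, 30 to 38 kg: 30/1.5625 = 19.2 to 38/1.5625 = 24.3, all in the class called normal.

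These heights are those of small children. The examples say nothing about patients aged 15-17.

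**3. How much can it matter?** In the overall column, no class can shift by more than (children with recorded BMI) / (patients in the denominator). Section 9.5.1 sets a minimum of 100 patients in the smallest country. With 0 or 1 such child:
- denominator 100: 0 to 1/100 = 1.0 percentage point;
- denominator 50 (assuming only half the patients have a BMI and percentages are taken over those): 0 to 1/50 = 2.0 percentage points.

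In the under-18 column the share affected could be large, but the number of patients is unknown. Section 7 describes the drug class as approved for adults, so there may be very few children or none. Table 9.4.5-1 shows BMI available in every candidate database except the Swedish registers, where the row would be entirely missing.

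**The case against.** The strongest reply is that this is a detail of a table shell. Section 9.7.5 leaves table shells to the statistical analysis plan, which is not at hand, and the note under Table 9.7.4-1 allows the layout to change. The label is printed beside its own cut-offs, so a reader sees what was counted. The paediatric column already carries the continuous BMI summary. The mock table is headed for Sweden, which has no BMI, so it must be adapted in any case. No evidence shows that a small child will start this drug.

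Much of this stands, and it is why the point is minor. It does not remove the point. The Protocol does not leave the classes open: it fixes the bins in the definitions table and the label in the mock table. Section 9.7.5 ties the later shells to the variables specified in the Protocol, and the note speaks of structure, so neither supplies an age rule. The Protocol does condition a threshold on patient type elsewhere: the creatinine cut-offs in Table 9.3.2-1 differ by sex.

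A reader might infer more: that the paediatric or off-label results are unsound, or that the overall BMI distribution is distorted. The documents do not support this. Under section 9.3 the under-18 subgroup is defined by age, off-label use by diagnosis and prior treatment, and medication error by doses per week. None uses BMI. Nor does it follow that the four age bands must be tabulated separately for BMI. Countries and years are not pooled (section 9.7.1), and a band with one patient would show only that patient's value.

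**Conclusion.** The point holds as a minor one. As written, a row that describes weight status, with a class called normal, applies without an age limit to a pre-specified subgroup that extends down to 0-4 years, and in younger children the classes do not describe weight status.

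The size is one descriptive row in databases with BMI. It moves a class in the overall column by at most 1.0 percentage point with one child in 100, or 2.0 with an assumed denominator of 50, and by nothing if there are no children. The conclusion rests on the general clinical fact that BMI changes with age in childhood. The heights and weights above only illustrate it. It should not be extended to older adolescents on this evidence.

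**What to change.** Restrict the BMI classes in Tables 9.3.2-1 and 9.7.4-1 to patients aged 18 or over. Use the adults in each column as the denominator and keep the line for missing values. For patients under 18, show only the continuous summary already in the block (n, mean and SD, median, range), without the classes or the 'Normal' label. A split by age band, or age- and sex-specific classes from a named reference, is optional if numbers allow.

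The cost is a row label and a footnote, with no new variables. The downside is that the class denominator differs slightly from the column N. With one child among 100 patients, a class of 50 adults reads 50/99 = 50.5% instead of 50/100 = 50.0%.
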